76 To support the evaluation of safety concerns regarding esomeprazole use, a study is proposed to
77 provide further evidence as to whether being prescribed esomeprazole is associated with an increased
78 risk of SD when compared to: (a) being prescribed alternative treatments from the same drug class
79 (i.e., other PPIs); (b) being prescribed alternative treatments from the other drug class (i.e.,
80 histamine type 2 receptor antagonists (H2RAs)); and (c) not being prescribed PPIs or H2RAs despite
81 indications for them (non-initiators). The rationale for using multiple comparator groups is based on
82 the fact that some of the available alternative treatments - which are preferable because of their
83 similar indication (active comparators) - have SD listed as a possible side effect. Ideally, the active
84 comparator should be known to have no effect on the event of interest since it is used to represent the

85 background risk in the disease. (Yoshida et al., 2015) However, impotence is listed as a rare side effect
86 for lansoprazole as well as for H2RAs, and decreased libido is listed as rare side effect for famotidine.
87 (EMC, 2024a, 2024b, 2024c) Therefore, we will opt to also include a non-user comparator (non-
88 initiators), to gain insight into the background risk for sexual dysfunction. Of note, the safety concerns
89 also included omeprazole (i.e. the racemate of esomeprazole and R-omeprazole) considering the partly
90 identical structure shared by esomeprazole and omeprazole. Hence, this study will also examine
91 whether being prescribed omeprazole is associated with an increased risk of SD when compared to the
92 abovementioned comparators.

93 In view of the differences in the definition of SD and risk factors between female and male individuals,
94 and the reported cases which occurred mostly in men and that the majority of primary care recording
95 of SD occurs in males, this study will focus on SD in male individuals only.

96

97 **3. Research question and objectives**

98 Among male patients, is the prescription of:

- 99 1) **Esomeprazole** associated with increased risk of sexual dysfunction (SD) when compared to
100 patients who are:
- 101 a) prescribed other PPIs (namely omeprazole, pantoprazole and lansoprazole)?
102 b) prescribed H2RAs?
103 c) not prescribed either PPIs or H2RAs?
- 104 2) **Omeprazole** associated with increased risk of sexual dysfunction when compared to patients
105 who are:

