- 106 a) prescribed other PPIs (namely esomeprazole, pantoprazole and lansoprazole)?
107 b) prescribed H2RAs?
108 c) not prescribed either PPIs or H2RAs?

109 Box 1 provides the rationale for the selection of multiple comparator groups.

110

Box 1. Rationale for the selection of multiple comparator groups and limitations

A. Active comparators (other PPIs, H2RA)

- Active comparators are alternatives for the target treatment within the same indication. They enable to indirectly restrict the study population to patients with a comparable indication to the target drug. If alternative treatments for the same indication can be identified and are assumed to be used interchangeably, i.e., prescribed with clinical equipoise, then confounding by indication is reduced.
- For this study, the most suitable active comparators would be either other PPIs or H2RAs which have similar indications. However, some shortcomings should be considered.
 - Lansoprazole and pantoprazole are the most common PPIs prescribed in the selected databases after esomeprazole and omeprazole. However, lansoprazole has already listed in the product information erectile dysfunction as a rare effect. Yet, the comparison with other PPIs might provide insights into whether any association observed is a class effect.

- H2RAs also have erectile dysfunction listed in the product information as a rare side effect and famotidine has also decreased libido listed. Yet, the comparison with H2RAs might provide insights into whether there is an increased risk of sexual dysfunction in esomeprazole/omeprazole users.
- The availability of over the counter (OTC) PPIs has increased over time and, subsequently their OTC use, which are not captured in electronic health records databases. Hence, exposure misclassification is expected.
- The prescribing of H2RAs has decreased over time (see Annex II, Excel file), particularly after the suspension of all ranitidine medicines in the European Union due to the presence of low levels of an impurity called N-nitrosodimethylamine (NDMA) in April, 2020.
- Other treatment alternatives which could have been considered as active comparators such as alginates - which are indicated for treatment of peptic ulcers, dyspepsia, mild forms of GERD, etc. as an adjunct to other drugs - are greatly used OTC. Thus, the potential for exposure misclassification may be greater than for H2RA considering their wide use.

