Box 2. Summary of study methods

	matched on birth-year. This date will be the non-initiator comparators index-date . Thus, with regards to treatment, the active treatment arms initiate a treatment on index-date and non-initiator comparators do not.
Outcome	First recorded occurrence of SD, including the following ICD-10 codes: F52.0, F52.1, F52.2, F52.3, F52.6, F52.8, F52.9, N48.4, N94.1, N48.3 [See section 4.6, Outcome]
Follow-up	Patients will be followed-up from index-date up to maximum 1 year. Thus, patients will be followed-up from index-date to the earliest of: date of first occurrence of outcome, loss to follow-up, death (only available in IMRD UK), end of follow-up (1 year) or end of the study period [See Section 4.5, Follow-up period]
Casual contrast of interest	Intention to treat effect, i.e., patients were followed up irrespective of treatment change (main analysis).
Statistical methods	
• Inverse probability of treatment weighting (IPTW) will be used to adjust for confounders measured at cohort entry.• Incidence rates (IR) and cumulative incidence proportions will be estimated for each treatment cohort.• Hazard ratios (HRs) will be estimated using a Cox proportional hazards model.• Cumulative incidence proportions will be estimated for each treatment arm using the Kaplan-Meier estimator.• Sensitivity analyses will include a "Per-protocol" analytical strategy and adjusting for informative censoring at treatment protocol violation. 
[See Section 4.7. Statistical analyses]

115

116

117 4.1. Study design

118 Comparative cohort design, including:

119 a) Active comparator, new user design:

120 • Esomeprazole initiators (target treatment [Cohort 1]) will be compared to the following
121 comparators: pantoprazole [Cohort 3], lansoprazole [Cohort 4], and H2RAs [Cohort 5]
122 initiators.

123 • Omeprazole initiators (target treatment [Cohort 2]) will be compared to the following
124 comparators: pantoprazole [Cohort 3], lansoprazole [Cohort 4], and H2RAs [Cohort 5]
125 initiators.

126 Treatment initiation will be defined as the prescription date for PPIs/H2RAs after a washout
127 window of at least 365 days in which no previous prescription with any PPIs or H2RAs have
128 been recorded. This date will coincide with the cohort entry or start of follow-up in the study,
129 which we will refer to as **index-date**.

130 b) Non-initiator comparator

[figure not shown]

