263 Table 2 summarises the treatment assignments by cohorts.

264

265 **Table 2.** Treatment assignment by cohorts.

Target treatments:	Active comparators:	Non-initiator comparator:

 • Treatment initiation as monotherapy* with: 
 ○ Esomeprazole [Cohort 1] 	
 • Treatment initiation as monotherapy* with: 
 ○ Selected PPIs: 	
 • Prior diagnosis of indication but no treatment

Target treatments:	Active comparators:	Non-initiator comparator:

 ○ Omeprazole [Cohort 2] 	
 ▪ Omeprazole [Cohort 2], when esomeprazole is the target treatment; ▪ Esomeprazole [Cohort 1], when omeprazole is the target treatment; ▪ Pantoprazole in IQVIA™ DA Germany [Cohort 3], or ▪ Lansoprazole in IMRD UK [Cohort 4] ○ Selected H2RAs [Cohort 5]: ranitidine, famotidine, cimetidine, nizatidine in IQVIA™ DA Germany, and ranitidine, famotidine, nizatidine, cimetidine in IMRD UK. 	
initiation with either PPIs nor H2RAs within previous 12-month or on index date [Cohort 6].

266 * **Note:** Treatment initiation with any combination with other PPIs or H2RAs on the index-date is not part of the
267 study.

268
269 **Outcome**

270 Sexual dysfunction (SD) will be defined as the first recorded occurrence of any of the following
271 conditions (ICD-10 code): lack or loss of sexual desire (F52.0); sexual aversion and lack of sexual
272 enjoyment (F52.1); failure of genital response (F52.2); orgasmic dysfunction (F52.3); nonorganic
273 dyspareunia (F52.6); other sexual dysfunction, not caused by organic disorder or disease (F52.8);
274 unspecified sexual dysfunction, not caused by organic disorder or disease (F52.9); impotence of
275 organic origin (N48.4); dyspareunia (N94.1), priapism, painful erection (N48.3).

276 **Annex 2** provides the list of WHO ICD-10 codes used to identify outcome events in IQVIA™ DA
277 Germany. READ codes were used to identify these conditions in IMRD UK (Annex 2). Of note, SD as
278 defined here is mostly driven by erectile dysfunction/impotence, which is the most frequent condition
279 recorded in both databases.

280
281 **Potential confounding factors:**

282 Analyses will account for the following baseline covariates measure before index-date, which are

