299 washout) esomeprazole versus patients who: a) initiated other proton pump inhibitors (PPIs, namely
300 omeprazole, pantoprazole/lansoprazole); b) initiated histamine type 2 receptor antagonists (H2RA))
301 and c) patients who did not initiate treatment with either PPIs or H2RA but had received a diagnostic
302 for a PPI or H2RA indication (i.e. non-initiators comparators). Outcome events will be attributed to the
303 baseline treatment protocol regardless of treatment change during follow-up. (i.e., **intention-to-treat
304 analysis (ITT)**).

305

306 4.7.2. Descriptive analysis

307 Descriptive analyses will be performed to describe the study cohorts at baseline in terms of
308 demographic characteristics, lifestyle factors, potential indications, comorbidities, and history of
309 treatment with drugs commonly associated with sexual dysfunction.

310

311 4.7.3. Main statistical analysis

312 **Inverse probability of treatment weighting (IPTW)**

313 Inverse probability of treatment weighting (IPTW) will be used to render the assignment of study
314 treatments independent of the baseline measured covariates, thus minimising the potential
315 confounding effect of these covariates.

316 Using IPTW, the average treatment effect (ATE) in the entire study population will be estimated,
317 assuming that all important confounding variables have been accounted for. For each observation in
318 the study population, the IPTW is the inverse of the probability of receiving the observed treatment

319 conditional on all variables considered sufficient for confounding adjustment. In order to stabilize the
320 weights (i.e., less extreme weights, that are closer to the mean weight of one), the numerator of one
321 will be replaced by the marginal probability of receiving the observed treatment in the study population
322 (i.e., the proportion of observations in the study population with the respective treatment). (Hernan &
323 Robins, 2006) All analyses will then be conducted in the re-weighted population without additional
324 confounding adjustment on the assumption of no unmeasured confounding. To account for weighting
325 the population (essentially multiplying observations by the weight coefficient) robust standard error
326 estimators will be used (Hernan & Robins, 2020).

327 The distributions of baseline covariates before and after weighting was compared between

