359 Hazard ratios of sexual dysfunction associated with treatment of interest (esomeprazole) versus
360 comparators will be estimated using a Cox proportional hazards model.

361

362 **4.7.4. Sensitivity analysis**

363 The following sensitivity analyses will be performed to test the validity of the underlying assumptions
364 and the robustness of the study findings:

365 **Applying "per-protocol" (PP) approach:** In this analysis, the follow-up of patients will be censored
366 at the initiation of a PPI or H2RA other than the baseline treatment. Assuming that such censoring is
367 independent of the risk of SD (i.e., non-informative censoring), this analysis will estimate the
368 treatment effect had patients remained on the baseline treatment for the entire follow-up or
369 discontinued the baseline treatment but without initiating an alternative PPI/H2RA.

370 Thus, we will consider a patient to respect the baseline treatment protocol from index-date to the date
371 of crossing over to an alternative treatment arm. Patients will be censored at the earliest of the
372 following events: end of index-treatment, crossing over to an alternative treatment arm, first outcome
373 event date, loss to follow-up (e.g., transfer out date from the general practice in IMRD or end of
374 continuous observation of the patient by the practice in IQVIA™ DA Germany, or date of last data
375 collection from the practice), date of death or at the end of the study period.

376 This approach addresses the situation in which a patient initiates another PPI/H2RA after index-date,
377 which might be problematic if the other PPI/H2RA initiated after index-date and within the 1-year
378 follow-up might cause the outcome event instead of the baseline treatment.

379 It should be noted that the difference between the ITT and PP approach will lie in the follow-up period.
380 The same baseline conditions such as eligibility criteria and washout period before index-date were
381 applied for both analytical approaches.

382 **Adjustment for informative censoring at treatment discontinuation in the PP analysis:** In the
383 per-protocol analysis described above, patients will be censored when they initiate another treatment.
384 Implicit in the per-protocol analysis is an assumption that censoring is independent of the studied
385 outcome, so that this differential treatment selection should not introduce bias.

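### The within-class comparator is defined two ways: the other target drug counts as an 'other PPI' in Section 3, Table 2 and Section 4.7.1 but not in Section 4.1 or Box 2, and pooling is left open

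*Protocol*

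**What the plan says.** The protocol describes the within-class comparator in five places, and they fall into two groups.

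**Other target drug included**
- Section 3, objective 1a: "a) prescribed other PPIs (namely omeprazole, pantoprazole and lansoprazole". Objective 2a is the mirror: "a) prescribed other PPIs (namely esomeprazole, pantoprazole and lansoprazole".
- Section 4.6, Table 2, active comparators: "Omeprazole [Cohort 2], when esomeprazole is the target treatment" and "Esomeprazole [Cohort 1], when omeprazole is the target treatment".
- Section 4.7.1, written for esomeprazole only, lists the other PPIs as "omeprazole, pantoprazole/lansoprazole); b) initiated histamine type 2 receptor antagonists (H2RA".

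**Other target drug not included**
- Section 4.1 gives both targets the same active "comparators: pantoprazole [Cohort 3], lansoprazole [Cohort 4], and H2RAs [Cohort 5".
- Box 2 lists esomeprazole and omeprazole (Cohorts 1 and 2) as target arms only. Its comparator arms are Cohorts 3 to 6: pantoprazole, lansoprazole, H2RAs and non-initiators.

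Three further statements bear on the point. The Background explains that the safety concerns "also included omeprazole (i.e. the racemate of esomeprazole and R-omeprazole) considering the partly" identical structure of the two drugs, and it says that an active comparator should ideally have no effect on the event. Box 1 says the comparison with other PPIs may help show whether an association is a class effect. In Section 4.7.3 the Cox paragraph speaks only of "Hazard ratios of sexual dysfunction associated with treatment of interest (esomeprazole) versus" comparators, and the balance paragraph also names only esomeprazole.

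**The concern.** The two groups of passages put different patients in the reference group for objectives 1a and 2a. This is current text at the level of the objectives. A statistical analysis plan could say how the arms are combined, but it could not pick one definition without overriding part of the protocol.

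One of the two definitions uses as reference a drug that the protocol itself places under the same suspicion. The protocol discusses openly that lansoprazole and H2RAs have listed sexual side effects. It does not discuss using one target drug as comparator for the other.

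What is at stake is how the within-class result can be read. If omeprazole carries some of the effect, then an estimate near 1 from a pooled contrast, or from the esomeprazole–omeprazole pair, cannot separate no effect from an effect shared by the two targets.

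**Working it through.** The protocol gives no event count, effect size, power or number of users per drug, so there is no figure of its own to reproduce. The check has two parts.

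**1. Is the comparator pooled or pairwise?** The text points both ways.
- Section 3 and Section 4.7.1 name the other PPIs as one category, which suggests a single group.
- Each PPI has its own cohort number, Table 2 lists them on separate lines, and Section 4.7.3 reports rates and cumulative incidence by treatment arm. In Box 2 only the H2RAs are said to be combined. This suggests pairwise contrasts.

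Neither reading is stated as the rule.

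**2. How much would it matter?** Take pantoprazole or lansoprazole as the reference (hazard 1). For an uncommon outcome and balanced covariates, the hazard in a pooled comparator is approximately a weighted average, so

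HR(pooled) = HR_eso / (w × HR_ome + 1 − w),

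where w is the omeprazole share of the pooled comparator.

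Inputs, all assumptions and none from the protocol:
- HR_eso = 1.5.
- HR_ome = 1.5 (fully shared effect), 1.25 (half the excess) or 1.0 (no effect).
- w = 10%, 50% or 90%.

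Worked example at w = 50%, fully shared: 1.5 / (0.5 × 1.5 + 0.5) = 1.5 / 1.25 = 1.20. With half the excess: 1.5 / (0.5 × 1.25 + 0.5) = 1.5 / 1.125 = 1.33.

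| Omeprazole effect | w = 10% | w = 50% | w = 90% |
|---|---|---|---|
| Fully shared (1.5) | 1.43 | 1.20 | 1.03 |
| Half the excess (1.25) | 1.46 | 1.33 | 1.22 |
| None (1.0) | 1.50 | 1.50 | 1.50 |

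With HR_eso = HR_ome = 2.0, the values at the same shares are 1.82, 1.33 and 1.05.

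If omeprazole's excess were larger than esomeprazole's, the contrast could pass 1. At 125% of the excess (HR_ome = 1.625) and w = 90%, it is 1.5 / (0.9 × 1.625 + 0.1) = 1.5 / 1.5625 = 0.96.

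Mirror case, objective 2a: omeprazole is the target, and esomeprazole is assumed to be 5% to 25% of the pooled comparator with a fully shared effect. The HR is 1.5 / (0.05 × 1.5 + 0.95) = 1.46 down to 1.5 / (0.25 × 1.5 + 0.75) = 1.33.

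Pairwise case: esomeprazole versus omeprazole is 1.5 / 1.5 = 1.00 if the effect is fully shared and 1.5 / 1.25 = 1.20 with half the excess. Esomeprazole versus pantoprazole or lansoprazole stays at 1.50.

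**On the share.** Section 4.6 leaves one remaining PPI comparator per database, and Box 1 ranks lansoprazole and pantoprazole behind the two target drugs in prescribing. Read literally, this makes a share above 50% plausible for objective 1a, but the protocol gives no counts, so the share stays an assumption.

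**The case against.** A reader might infer that including omeprazole in itself pulls the within-class contrast toward 1. The documents do not support that without conditions. It needs a pooled comparator, which the protocol never states and which the separate cohort numbering speaks against. It also needs omeprazole to carry part of the effect. The larger attenuations further assume a high omeprazole share and an equal effect in both drugs. With separate arms, the contrast with pantoprazole or lansoprazole is unaffected. This part of the objection stands, and the size can only be given as a conditional range.

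A second argument is that the design does not rest on this contrast alone. Box 1 and Section 4.9 add non-initiators because active comparators may carry the effect themselves, and an effect shared by both targets could still show in objectives 1b, 1c, 2b and 2c. This stands in part. By the protocol's own account, however, H2RAs have erectile dysfunction listed, and non-initiators may include over-the-counter users and differ in unmeasured risk factors.

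Third, lansoprazole is not a clean reference either, since impotence is listed for it. That is correct and should be said with the result. It does not settle which patients belong in the comparator.

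The esomeprazole-only wording of the Cox and balance paragraphs is editorial. The omeprazole contrasts are set out in Section 3, Section 4.1 and Table 2.

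**Conclusion.** The contradiction is certain and runs in both directions: the reference group of objectives 1a and 2a is defined in two incompatible ways, and the protocol does not say whether the PPIs are pooled.

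Attenuation is conditional. It follows if the PPIs are pooled and omeprazole shares some of the effect, and that sharing is the study's own reason for making omeprazole a target. Under an assumed true HR of 1.5, the esomeprazole estimate would then lie anywhere from about 1.46 (10% share, half the excess) to 1.03 (90% share, fully shared). The protocol does not allow a narrower range. A claim of established bias toward 1 would go beyond the text.

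What holds without any assumed size is the problem of interpretation. An estimate near 1 from a pooled contrast, or from the esomeprazole–omeprazole pair, would be ambiguous for the class-effect question that Box 1 assigns to this comparison. The H2RA and non-initiator contrasts relieve this only partly.

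**What to change.** - Reconcile Section 3, Box 2, Section 4.1, Table 2 and Section 4.7.1 so that each target drug has one stated within-class comparator.
- Define that comparator as pantoprazole in the German database and lansoprazole in the UK database, and note lansoprazole's own listed effect where the result is interpreted.
- Report esomeprazole versus omeprazole as a separate, labelled contrast that is never pooled into the other PPIs.
- As an editorial alignment, word the Cox and balance paragraphs of Section 4.7.3 for both target drugs.

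The cohorts are already numbered separately, so no new cohort is needed. The change does reword objectives 1a and 2a. The statistical price is a smaller comparator group, and so a somewhat wider interval, than a pooled comparator would give.

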- 131 • Esomeprazole initiators (target treatment [Cohort 1]) will be compared to patients who
132 did not have a prescription for either PPIs or H2RA despite having a recorded indication
133 (see Section 4.3, eligibility criteria) for these treatment (non-initiator comparator
134 [Cohort 6]).
- 135 • Omeprazole initiators (target treatment [Cohort 2]) will be compared to patients who
136 did not have a prescription for either PPIs or H2RA despite having a recorded indication
137 (see Section 4.3, eligibility criteria) for these treatment (non-initiator comparator
138 [Cohort 6]).

139 As above, treatment initiation will be defined as the prescription date for
140 esomeprazole/omeprazole after a washout window of at least 365 days in which no previous
141 prescriptions with any PPIs or H2RAs have been recorded. This date will coincide with the start
142 of follow-up in the study, which we will refer to as **index-date**.

143 Non-initiator comparators will be selected on each date of the recruitment period when
144 esomeprazole/omeprazole initiators start treatment, matched on birth-year. This date will be
145 the non-initiator comparators index-date. Thus, with regards to treatment, the active
146 treatment arms initiate a treatment on index-date and non-initiator comparators do not.

147

148 A graphical representation of the study design including the assessment windows for inclusion-
149 exclusion criteria, covariates and follow-up relative to index-date is shown in Figure 1. Further details
150 for each component of the diagram are provided in the respective sections below.

151 **Figure 1.** Study design diagram.

152 Dx: diagnosis; Rx: prescription; SD: sexual dysfunction
 153 ^{a,b} Selected indications: GERD, gastric and duodenal ulcers, chronic forms of gastroduodenitis, and Zollinger-Ellison
 154 syndrome and recent comedication with NSAID, acetyl salicylic and derivatives, glucocorticoids, and antithrombotic
 155 treatments.
 156 ^c Selected severe CNS diseases: Hereditary ataxia (mainly hereditary spastic paraplegia), Huntington disease, spinal
 157 muscular atrophy and related syndromes, cerebral palsy, hemiplegia, paraplegia and tetraplegia, other paralytic
 158 syndromes (monoplegia of lower limb, cauda equina syndrome, locked-in syndrome), dependence on wheelchair.
 159 ^d Baseline conditions: See Section 4.6 on potential confounding factors.

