386 In this analysis, we will adjust for potential selection bias via informative censoring, by reweighting
387 patient observations using the inverse of the probability of being censored at the initiation of another
388 treatment conditional on the same confounders selected at baseline (i.e., outcome risk factors
389 potentially associated with treatment initiation) but updating their values during follow-up. (Hernan et
390 al., 2000; Robins et al., 2000)

391

392 Analyses will be done using SAS Enterprise Guide 7.1 software.

393

394 **4.7.5. Sample size**

395 The sample size will be driven by the availability of individuals with exposures and outcomes within
396 each database and no *a priori* sample size requirement will be stipulated.

397

398 **4.8. Quality control**

399 The study will be conducted according to the ENCePP code of conduct (European Medicines Agency
400 2018).

401 Standard operating procedures or internal process guidance will be adhered to for the conduct of the
402 study. These procedures include rules for secure and confidential data storage, quality-control
403 procedures for all aspects of the study from protocol development to the reporting of the results.

404 All documents will undergo at least one round a review by an experienced reviewer, while the results
405 from the statistical analysis will be either reviewed or checked via double coding.

406 The quality control of the data is the responsibility of the data holder.

407 **4.9. Limitations of the research methods**

408 Exposure misclassification may exist since neither OTC drug use nor medication use during
409 hospitalisation are captured in the included databases. This is a particular issue because of the availability
410 of OTC PPIs has increased over time (Johnson et al., 2017) and, probably their OTC use. Additionally,
411 information on the actual duration of treatment corresponding to each prescription is not available and
412 is difficult to estimate since patients may be prescribed large packs and instructed to use the drug as
413 needed, with possible discontinuation/restart and dose-variation over time. Moreover, whether patients
414 collected their prescriptions or consumed the prescribed medication is unknown. Due to this uncertainty
415 and considering information from individual case reports about the latency of effect, we chose to follow
416 patients for a maximum of one year and attribute the entire follow-up to the index treatment unless

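### Box 1 looks to the PPI comparison for insight into a class effect, but no hazard ratio is planned for pantoprazole, lansoprazole or H2RAs against non-initiators

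*Protocol*

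**What the plan says.** Box 1 (Section 3) explains the choice of several comparators. On the PPI arms it says that "the comparison with other PPIs might provide insights into whether any association observed is a class effect". It also says that lansoprazole and H2RAs already have erectile dysfunction listed as a rare effect. Non-initiators are added because the active comparators cannot show background risk.

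The contrasts are fixed in Sections 3, 4.1, 4.7.1 and 4.7.3:

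- Section 4.1(a), active comparators: "Esomeprazole initiators (target treatment [Cohort 1]) will be compared to the following" pantoprazole, lansoprazole and H2RA cohorts, and "Omeprazole initiators (target treatment [Cohort 2]) will be compared to the following" same three.
- Table 2 adds each target drug as a comparator for the other, for example "Omeprazole [Cohort 2], when esomeprazole is the target treatment".
- Section 4.1(b), non-initiators: "Esomeprazole initiators (target treatment [Cohort 1]) will be compared to patients who" had an indication but no prescription, and "Omeprazole initiators (target treatment [Cohort 2]) will be compared to patients who" meet the same description.
- Section 4.7.3, Cox model: "Hazard ratios of sexual dysfunction associated with treatment of interest (esomeprazole) versus" comparators.

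Incidence rates and cumulative incidence are planned for each cohort. On size, Section 4.7.5 says that "no *a priori* sample size requirement will be stipulated".

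**The concern.** A class effect means that the other PPIs also raise risk above background. The contrast that addresses this directly is pantoprazole or lansoprazole against non-initiators, and it is not planned. What remains is a two-step inference: esomeprazole or omeprazole is raised against non-initiators, and does not clearly differ from the other PPI. The second step leans on the absence of a difference, and the Protocol sets neither a margin nor a precision target for it.

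The active comparators raise the same difficulty more generally. Because lansoprazole and H2RAs may themselves carry risk, an HR near 1 against them fits both no risk and equal risk. The target drug's own non-initiator contrast helps to separate the two, but no estimate with an interval shows where the comparator stands relative to background. At stake is whether a signal specific to esomeprazole could be described as a class effect, or the reverse, on weak evidence.

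**Working it through.** **1. Contrast list.** Read across Sections 3, 4.1, Table 2, 4.7.1 and 4.7.3, the planned HRs against each reference are:

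| Arm | vs other PPI | vs H2RAs | vs non-initiators |
|---|---|---|---|
| Esomeprazole | yes | yes | yes |
| Omeprazole | yes | yes | yes |
| Pantoprazole (Germany) | only as comparator | no | **no** |
| Lansoprazole (UK) | only as comparator | no | **no** |
| H2RAs | – | – | **no** |

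Omeprazole is an other PPI when esomeprazole is the target, and it does have a non-initiator contrast. But Section 2 describes it as the racemate that includes esomeprazole, so it says little about the rest of the class.

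**2. What can be recovered from the planned results.** If all arms share one weighting, then approximately

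log HR(other PPI vs non-init.) = log HR(esomeprazole vs non-init.) − log HR(esomeprazole vs other PPI).

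This gives a point estimate but no correct interval, because the two HRs share the esomeprazole arm and their covariance is not reported. Take assumed events of 100 (esomeprazole), 500 (other PPI) and 1000 (non-initiators), with SE = √(1/d₁ + 1/d₂):

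- Direct contrast: √(1/500 + 1/1000) = 0.0548, so the 95% CI around HR 1 is 0.90 to 1.11.
- Difference of the two planned HRs, treated as independent: √(0.1095² + 0.1049²) = 0.152, giving 0.74 to 1.35.

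A reader working from the published HRs would therefore get a much wider interval than the data support.

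**3. How often a within-class null could mislead.** The Protocol gives no counts, so there is no stated figure to reproduce, and every count here is an assumption. Suppose the true HR against background is 1.25 for esomeprazole and 1.0 for the other PPI, with two-sided alpha 0.05. With d esomeprazole events and a comparator of k times the person-time, the comparator has k·d/1.25 events. The miss probability is 1 − Φ(log 1.25/SE − 1.96).

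Example with d = 100, k = 1: SE = √(1/100 + 1/80) = 0.150; 0.223/0.150 − 1.96 = −0.47; miss = 68%.

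| Esomeprazole events | Equal arms | Comparator 10× |
|---|---|---|
| 100 | 68% | 44% |
| 200 | 44% | about 15% |
| 400 | about 15% | 1% |

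If weighting inflates the variance by 1.5, these become 77% and 60%, 60% and 32%, and 32% and 7%. At a true HR of 1.5 with 100 events they fall to 27% and about 3%.

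The misleading pattern also needs significance against non-initiators. Given that, with non-initiators at 10×, the within-class test is still non-significant in 52% (100 events, equal arms), 37% (200, equal arms) and about 13% (100, comparator 10×).

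**4. Precision of the added contrast.** With 100 esomeprazole events and a tenfold other-PPI arm (800 events):

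- Esomeprazole vs other PPI: SE = √(1/100 + 1/800) = 0.106, 95% CI factor ×/÷1.23.
- Other PPI vs non-initiators, non-initiators 10× (800 events): SE = 0.050, factor ×/÷1.10.
- The same, non-initiators 1× (80 events): SE = √(1/800 + 1/80) = 0.117, factor ×/÷1.26.

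The added contrast is thus not always the more precise one. It depends on the number of non-initiators, and the Protocol gives no matching ratio.

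**The case against.** The strongest reply is that class effect is not a research question in Section 3. It appears in one tentative sentence of Box 1, which presupposes that an association has been seen. A reader might infer that the Protocol will declare a class effect whenever the within-class HR is non-significant; no text says so. Nor is a null the only informative result, since a clear difference from other PPIs would argue against a pure class effect. These points stand.

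It can also be said that background risk is already covered. Esomeprazole and omeprazole are each compared with non-initiators for exactly that reason, and the comparators are meant to be read together. A null against H2RAs with a raised HR against non-initiators points to shared risk; a null against both points to no detected risk. This stands for the target drugs, and rates for every arm allow an informal look at the comparators. What is missing is an estimate with an interval for the comparators themselves.

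A third objection is that non-initiators are a weak yardstick. Box 1 calls a non-user comparator not preferable for safety studies, and Section 4.9 warns of unmeasured differences. Such confounding could raise every treated arm together and look like a class effect. Non-initiator index dates also follow esomeprazole and omeprazole starts only, while H2RA prescribing fell over time. Both points stand and shape the fix. Age and calendar year are already adjustment covariates, so the contrasts are feasible if overlap is adequate.

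Finally, extra secondary contrasts could be left to an analysis plan. But the Protocol itself fixes the contrast list and names the insight sought from it, so the mismatch can be seen in this document.

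**Conclusion.** The point holds as a moderate gap between a stated interpretive aim and the planned contrasts. No figure is wrong. No HR or interval is planned for pantoprazole, lansoprazole or H2RAs against non-initiators, so a class effect or shared risk could be supported only indirectly.

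A reader might go further and infer that the within-class null will be imprecise. The document does not support this: it gives no arm sizes or event counts, and under the assumptions shown the miss rate runs from 77% down to 1%. The gap matters most if esomeprazole events number about 100 to 200 or the other-PPI arm is not much larger than the esomeprazole arm. It matters little with 400 or more events and a large comparator. These figures assume a normal approximation on the log-hazard scale and a true HR of 1.25 confined to esomeprazole.

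**What to change.** In Sections 4.1(b) and 4.7.3, add as secondary contrasts weighted Cox HRs with 95% CIs for pantoprazole (Germany), lansoprazole (UK) and H2RAs (both databases) against non-initiators. For these pairs, check balance and overlap of covariates, age and calendar time, because the non-initiator index dates were not drawn for those arms.

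In Box 1, state that:

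- a class effect will be judged from these HRs together with the PPI-versus-PPI confidence interval;
- an interval that includes 1 against an active comparator is not by itself evidence of a class effect or of no risk;
- raised HRs against non-initiators in all treated arms may also reflect the residual confounding described in Section 4.9.

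The cost is two more HRs per database from cohorts already being built, the balance checks and a few sentences. No new data are needed. The downside is a few more secondary contrasts against the less preferred comparator.
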